10.3.5	Monitoring	20
11	PARTICIPANT RIGHTS AND CONFIDENTIALITY	20
11.1	Institutional Review Board (IRB) Review	20
11.2	Informed Consent Forms	20
11.3	Participant Confidentiality.....	20
11.4	Study Discontinuation	21
12	ETHICAL CONSIDERATIONS	21
13	PUBLICATION OF RESEARCH FINDINGS.....	21
14	REFERENCES	21
15	APPENDIX	26
15.1	Changing Talk Online (CHATO) Implementation Toolkit.....	26
15.2	Changing Talk Online (CHATO) Training Overview	26
15.3	CHATO Implemenation Strategies Survey	26
15.3.1	Artifacts of Culture Change Survey	26
15.4	CHATO Leadership Inverviews.....	26

PRÉCIS

Study Title

Changing Talk Online (CHATO): A Pragmatic Trial to Reduce Behavioral Symptoms in Dementia Care (Pilot)

Objectives

AIM 1. Establish acceptability and preliminary efficacy of online CHATO modules through pilot testing with NH staff.

AIM 2. Develop and pilot test the data collection tool with consultant and advisory panel input. Interviews of NH administrators and staff who participate in the pilot testing of CHATO and a process evaluation will be used to identify and develop supports for implementation and sustainability in preparation for future CHATO testing.

Design and Outcomes

The R61 will prepare for the R01 pragmatic trial by establishing feasibility of online modules and preliminary efficacy of CHATO with NH staff. The research design is a randomized clinical trial. One NH will provide initial feasibility testing. Any modifications to the modules will be made. Then six nursing homes (estimated N=150 staff) will be randomly assigned to intervention or wait-list control groups. The primary outcome will be knowledge gain for staff completing CHATO training. Additional outcomes include facility level data related to resident quality measures of behavioral and psychological symptoms of dementia (BPSD) and inappropriate use of psychotropic medications to control BPSD. Implementation strategies will be assessed by survey and leadership interviews completed by an external evaluator.

Group	Time 1	1 Month	Time 2	1 Month	Time 3
Immediate 3 NHs	Baseline assessment ¹	CHATO training ²	Post-training assessment ³		
Wait list 3 NHs	Baseline assessment ¹		Repeat baseline assessment ¹	CHATO training ²	Post-training assessment ³

¹Pre-test knowledge, Communication rating; ²Three modules over a one-month period;

³Post-test knowledge, Communication rating, Program Evaluation, Diffusion of Innovation

Interventions and Duration

Changing Talk Online (CHATO) training is a course designed to increase awareness of the importance of effective communication with older adults and to use evidence-based person-centered communication during interactions with older adults in nursing homes and other health care settings. The total program is approximately 3 hours, split into 3 modules. Each module is approximately an hour, depending on the individual user. Each NH will work with the research team for three months to plan, implement, and collect data.

Sample Size and Population

This course is designed for staff in nursing homes, independent and assisted living, and health care settings in the community that include registered nurses, nursing assistants, nursing home dieticians, direct care professionals, other administrations and support employees. All the employees at all seven nursing homes will be asked to participate. Assignment of NHs to intervention and wait-list control groups will be at random. We estimate a total sample of 150 training participants.

STUDY TEAM ROSTER

Principal Investigator: **[name], PhD, FNP-BC, FGSA, FAAN**

[name] Professor
University of Kansas School of Nursing
[name]
Kansas City, KS 66160
[contact]
[contact]

Main responsibilities: Research Lead

Co-Investigators:

[name]
University of Kansas School of Nursing
[name]
Kansas City, KS 66160
[contact]
[contact]

Main responsibilities: Project Director

Co-Investigators:

[name]
University of Iowa School of Nursing
[name]
Iowa City, Iowa 52242
[contact]
[contact]

Main responsibilities: Statistician

Co-Investigators:

[name]
University of Iowa College of Public Health
[name]
Iowa City, Iowa 52242
[contact]
[contact]

Main responsibilities: Instructional Designer

Study Personnel:

[name], MSW
Office of Nursing Research and Scholarship
[name]
Iowa City, IA 52242
[contact]
[contact]

Main responsibilities: Data Manager

Study Personnel:

[name], BA
University of Iowa College of Public Health
[name]
Iowa City, Iowa 52242
[contact]

[contact]

Main responsibilities: Learning System Coordinator

Study Personnel:

[name], MSN

University of Iowa School of Nursing

[name]

Iowa City, Iowa 52242

[contact]

[contact]

Main responsibilities: Graduate Research Assistant

Consultant:

[name]

Senior Vice President of Research, LeadingAge and Co-Director,

1 STUDY OBJECTIVES

1.1 Primary Objective

AIM 1. Establish acceptability and preliminary efficacy of online CHATO modules through pilot testing with NH staff.

1.2 Secondary Objectives

AIM 2. Develop and pilot test the data collection tool with consultant and advisory panel input. Interviews of NH administrators and staff who participate in the pilot testing of CHATO and a process evaluation will be used to identify and develop supports for implementation and sustainability in preparation for future CHATO testing.

2 BACKGROUND AND RATIONALE

2.1 Background on Condition, Disease, or Other Primary Study Focus

The population afflicted with Alzheimer's disease and other dementias will expand from 5 to 16 million by 2050, increasing dementia care costs from \$259 billion to \$1.1 trillion.¹ Of today's 1.4 million nursing home (NH) residents, 61% have moderate to severe dementia, and up to 90% of them exhibit behavioral and psychological symptoms of dementia (BPSD) such as physical and verbal aggression, agitation, and wandering.^{2,4} These behaviors are associated with depression as well as reduced quality of life and lower survival rates in persons with dementia (PWD).³ BPSD also stress family caregivers and precipitate NH placement.^{5,6} In the NH, BPSD increase time to provide care, and NH staff, primarily Certified Nursing Assistants (CNAs) who provide most direct care, report that BPSD represent the most stressful aspect of their job.⁷⁻⁹ Considering additional costs for CNA burnout and turnover, It is estimated that BPSD increase costs of dementia care by 25 to 35%.¹⁰ With national NH rates for a semi-private room of \$82,200 per year, reducing BPSD may save up to \$20,000 per resident annually.¹¹

As cognitive and communication abilities decline due to dementia, NH residents become unable to convey care preferences and needs and staff communication becomes infantilizing, impersonal, and task-oriented resulting in BPSD. As verified in our research using behavioral coding and sequential analyses of video-recorded care, staff elderspeak (communication that sounds like baby talk) is linked to resident resistiveness to care (RTC), a subset of BPSD that disrupt nursing care. In our study, NH residents were more than twice as likely to be resistive to care when staff used elderspeak compared to normal communication.¹² Thus, improving communication has great potential as a nonpharmacological intervention to reduce BPSD in NH care.¹³

2.2 Study Rationale

The Communication Predicament of Aging theory establishes the link between elderspeak and BPSD. Elderspeak derives from stereotypical views of older adults as less competent than younger persons.¹⁴ When younger people talk with older adults, they modify their speech by simplifying, clarifying, and altering the underlying affective quality of messages.^{15,16} The resulting implicit message of incompetence begins a negative feedback loop for older persons, who react with depression, withdrawal, and dependency.¹⁴ Elderspeak is especially threatening to self-concept and personhood, critical to the wellbeing of PWD who are likely to respond with BPSD.^{17,18} The Need-driven Dementia-compromised Behavior model recognizes BPSD as the expression of unmet needs of PWD.^{19,20} Communication, that staff can modify to prevent BPSD, is an essential constant part of the environment connecting PWD to others and affirming their self-concept.

Psychotropic medications are often used inappropriately to control BPSD in NH residents with dementia.^{21,22} Alarmingly high rates persist, despite negative outcomes,²³ an FDA black box warning of increased mortality for older adults with dementia,²¹ and a recent Centers for Medicare and Medicaid Services (CMS) mandate to reduce off-label prescribing of antipsychotics.²⁴ CMS and the National Partnership to Improve Dementia Care target reductions in psychotropic drug use as top priority.²⁵ Despite reductions in antipsychotic rates (one type of psychotropic medication) ranging from 3 to 12% from 2011-2016, up to 20% of NH residents received inappropriate antipsychotic medication in 2017.²⁶ Research demonstrates that educating direct care providers in behavioral interventions to control BPSD also reduces psychotropic drug use (antipsychotics, hypnotics, antidepressants, antianxiety, sedative, anticonvulsant and mood stabilizers),²⁷⁻²⁹ although evidence is limited by lack of rigorous clinical trials that also evaluate approaches that influence intervention effects.²⁷

Our recently completed R01 clinical trial that tested Changing Talk (CHAT) communication training (NR011455) provides preliminary data for the proposed research. CHAT decreased staff elderspeak that reduced resident RTC.³⁰ On average, elderspeak declined from 34.6% (SD = 18.7) at baseline by 13.6 percentage points (SD = 20.00) post-intervention and 12.2 percentage points (SD=22.0) after 3 months (see Figure 1). RTC declined from 35.7% (SD = 23.2) by 15.3 percentage points (SD = 32.4) post-intervention and 13.4 percentage points (SD=33.7) at follow-up. Linear mixed modeling determined that change in elderspeak was predicted by CHAT ($b = -12.20, p = .028$) and baseline elderspeak ($b = -0.65, p < .001$), while RTC change was predicted by elderspeak change ($b = 0.43, p < .001$), baseline RTC ($b = -0.58, p < .001$), resident communication disability, and comorbid illnesses.

[figure not shown]

Figure 1. CHAT effects on elderspeak & RTC.

CHAT increases staff awareness of elderspeak's negative effects and guides practice of more effective communication. CHAT includes three, hour-long sessions, with replicated effects on communication in three studies among staff (N=89) and residents (N=194) in over 20 NHs.³⁰⁻³² Effect sizes ranged from $\eta^2 = .35$ to $.62$ for reducing elderspeak diminutives (inappropriately intimate terms of endearment) and collective “we” pronoun substitutions; effects were maintained

over 2 months. Person-centered (vs task-focused) communication also increased.^{30,33} CHAT was highly rated by past participants (N=217); mean program ratings ranged from 4.5 to 4.8 on a 1 (low) to 5 (high) scale.³⁴

To evaluate the potential impact of CHAT on psychotropic medication use, we extracted CMS NHQM data for use of antipsychotics for the 10 CHAT NHs for which data were available. We compared each NH's rates for two quarters before and two quarters after each participated in CHAT. The percentage of residents prescribed antipsychotics decreased by an average of 4.9 percentage points, from 20.7% (SD=8.5) to 15.8% (SD=9.0) after CHAT. We used state average rates of antipsychotic medication use for the same time periods to control for changes that may have occurred due to the CMS mandate and other factors.⁴⁷ The state benchmark for prescribed antipsychotics averaged 25.4% across quarters before and declined to 24.9% for quarters after CHAT, a decrease of 0.5%. The average decrease in CHAT NHs (4.9%) compared to the other state NHs (0.5%) was significant ($p=0.05$ for two-tailed t-test).⁴⁸

Despite the success of CHAT in reducing elderspeak and RTC, we found challenges to educating NH staff that limited participation in CHAT including turnover, absenteeism, heavy workloads, and personal conflicts.^{35,36,37} Each CHAT session was held multiple days and times. Still, as few as 44% of staff in one NH completed at least two of the three sessions,³⁰ although this rate is higher than that noted for other NH staff training programs.³⁸ Although successful in reducing RTC, the classroom format limits staff access and participation and feasibility for widespread dissemination. Creative, efficient approaches are needed to overcome NH staff education barriers.^{39,40} We first evaluated online web conference training with multiple NHs as an alternative format for increasing access and dissemination.⁴¹ However, engagement of individual staff was limited with this approach. To facilitate dissemination, online CHAT modules (CHATO) were developed to provide the same CHAT content with asynchronous and independent access for busy NH staff.³⁷

The PI worked with an instructional designer, item writer, and media team to transition CHAT content, including 20 video clips of NH staff-resident interactions, to the online CHATO modules.³⁷ Scripts from the original CHAT were narrated to maintain content, integrating adult learning theories and principles for online learning, and eliminating a need for advanced literacy skills. Interactive scenario and game-based activities engage staff. For example, participants watch a video clip, select problem communication in the transcript, type their improved communication, and compare it to suggested corrections. Moderated online discussions are included in the modules that are supported on Training-Source.org, a free and publicly available learning portal.

IT functionality and content equivalency of the newly developed CHATO online modules was demonstrated by a convenient university-affiliated sample of nurses, CNAs, and students (N=9) with NH experience. They rated the online modules at 4.7 to 5.0 on a 1 to 5 scale (1 = strongly disagree to 5 = strongly agree) for increasing their knowledge, usefulness, clarity, and satisfaction. CHATO was rated as easy by 57%, while 43% found it somewhat challenging but not too difficult. All reported moderate to great improvement in recognizing and understanding ineffective communication and developing effective communication skills.³⁷ Pre to post test scores improved from $M = 82.4\%$ (SD 10.62) to $M = 91.21\%$ (SD 8.22). Effect sizes for pre-post changes for identifying ineffective, appropriate, and person-centered communication in a video clip were greater for CHATO participants compared to past CHAT participants (N = 217).^{34,37} Although the group testing CHATO may not represent all NH staff, findings confirm that CHATO is feasible and comparable in content and effects.

While CHAT effectively reduced RTC, the in-person classroom format required an onsite interventionist, which limits accessibility and feasibility for dissemination. A pilot test of

acceptability and preliminary efficacy of online CHATO modules is the next logical step. The pilot will prepare for a pragmatic clinical trial that will test the effects of improved staff communication (from CHATO) on resident BPSD, using available clinical Minimum Data Set (MDS) data. Effects on psychotropic medication use, measured by MDS and Nursing Home Quality Measures (NHQM) data, will also be evaluated. This research will address the gap in rigorous trials testing nonpharmacological interventions to decrease BPSD that also identify strategies to improve intervention dissemination.²⁷ The goal is to increase access to CHATO training, as a tool to reduce BPSD and inappropriate psychotropic medication use to improve dementia care.

3 **STUDY DESIGN**

The R61 will prepare for the R01 pragmatic trial by establishing feasibility of online modules and preliminary efficacy of CHATO with NH staff. The research design is a randomized clinical trial. One NH will provide initial feasibility testing. Any modifications to the modules will be made. Then 6 nursing homes (estimated N=150 staff) will be randomly assigned to intervention or wait-list control groups. The primary outcome will be knowledge gain for staff completing CHATO training. Additional outcomes include resident quality measures related to behavioral and psychological symptoms of dementia (BPSD) on both resident and facility levels and facility level data related to inappropriate use of psychotropic medications to control BPSD.

Staff Knowledge Gain. At time 1, nursing home staff in both groups will complete baseline pre-tests of knowledge and rating of communication. The immediate intervention group will then complete the online CHATO modules within a one-month period. This includes assessments of post-test knowledge, communication rating, program evaluation, and diffusion of innovation surveys at Time 2. Also, at Time 2, the wait-list control group will repeat the pre-tests of knowledge and communication rating and will then complete the CHATO online module training over a one-month period, followed by Time 3 collection of post-test knowledge, communication rating, program evaluation, and diffusion of innovation surveys. Knowledge gain and communication rating data will be compared between the intervention and wait-list control groups and within nursing homes before and after the CHATO training. Changes in knowledge from Time 1 (baseline) to Time 2 will be compared between immediate and wait-list groups using model estimates obtained with a linear mixed model (LMM) approach to account for repeated measures and clustering within nursing homes. Next, pre- to post-training changes in knowledge will be combined for immediate and wait-list groups and also tested using LMM approach. The models will be adjusted for covariates, such as staff role (RN, LPN, CNA, other), experience, and whether the nursing home has a SCU or not.

TABLE 1. R61 Study Design

Group	Time 1	1 Month	Time 2	1 Month	Time 3
Immediate 3 NHs	Baseline assessment ¹	CHATO training ²	Post-training assessment ³		
Wait list 3 NHs	Baseline assessment ¹		Repeat baseline assessment ¹	CHATO training ²	Post-training assessment ³

¹Pre-test knowledge, Communication rating; ² Three modules over a one-month period;

³ Post-test knowledge, Communication rating, Program Evaluation, Diffusion of Innovation

Resident Quality Measure Outcomes. In addition, nursing homes in both groups will provide monthly summary reports for behavioral symptom occurrence for the facility (in aggregate as well as for individual residents [deidentified]). A nursing home aggregate antipsychotic medication use report will also be collected and analyzed. The BPSD and medication reports will

be provided for the one-month period before baseline data collection and for each month thereafter until the post-training assessment of the wait-listed nursing homes is completed (a total of seven months for both groups). Resident outcomes data will be compared between the intervention and wait-list control groups and within nursing homes before and after the CHATO training. Seven months of data will be plotted to examine changes in nursing homes and resident outcomes.

Implementation Strategies and Process Evaluation. An Implementation Toolkit for NHs and a CHATO Training Manual (See Appendices) have been created to provide support and implementation suggestions to pilot nursing homes. Several consultants provided feedback and additional resources to be included in these materials. Each NH will be given a three-month period to complete the CHATO training. One month for orientation, team development, and planning, one month to complete the three-week training, and one month for staff recognition and follow up. The CHATO Research Team will meet with the NH leadership at the beginning and end of this three-month period, manage CHATO training virtual discussion board, and provide technical assistance as necessary. The process evaluation includes an online implementation survey (See Appendices) which identifies the strategies NHs used to implement the training and includes the Artifacts of Culture survey. The survey uses the Diffusion of Innovation framework and mirrors the Implementation Toolkit. Additional process evaluation activities include: Leadership phone interviews completed by the consultants and external evaluators at LeadingAge and open-ended questions asked of direct care staff in the CHATO virtual discussion.

TABLE 2. R61 Research Timeline

	Quarter 1	Quarter 2	Quarter 3	Quarter 4	Quarter 5	Quarter 6
Planning (IRB, DSMB, Manuals, Measurement)						
Pilot CHATO Modules	—	—	—	—		
Analyses:		—	—	—		
Knowledge Gained			—	—		
Process Evaluation			—	—		
Resident Outcomes			—	—		
Dissemination			—	—	—	—

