The CHATO program is presented in three modules.^{37,63} Session 1 introduces effective versus ineffective communication. Participants identify communication issues in video vignettes. Session 2 focuses on identification and negative effects of elderspeak, using video-recorded

examples. Session 3 includes strategies for improved communication based on assessment of each resident's abilities. Participants critique communication in videos and correct transcripts to eliminate elderspeak. Training is limited to three, 1-hour sessions to assure feasibility in busy NHs. The modules include interactive exercises that must be successfully completed to advance through the program, assuring delivery of content fidelity and dose of the intervention. CHATO is provided to as many staff as possible to achieve facility-wide effects of reduced elderspeak.⁶⁷

NH sites will receive the link to the trainings in three-month intervals according to the randomization plan. The NH leadership will determine the best method of implementation for their site. The link to the training will be shared with staff and the staff will have three months to complete all three modules. The modules contain pre and posttests (scenario-based questions and rating of staff communication in video clips) to evaluate knowledge gain from CHATO. The Modified Duke Diffusion of Innovation⁵⁸ survey provides information about CHATO participant intentions to use learned skills in practice and the likelihood for translation.

During the R61, the instructional designer will assure that data for identifying each participant's NH and metrics including time spent in each module are collected for analyses.^{34,37}

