6.2.3 Treatment: CHATO Training

The treatment schedule may vary according to the needs of each individual nursing home; however, all modules will be completed by as many staff as possible during the three-month intervention period. Technical assistance will be provided as needed.

- Treatment: CHATO Training Module 1
 - Staff Demographics
 - Communication Rating Sheet Pre-Test
 - CHATO Knowledge Pre-Test
- Treatment: CHATO Training Module 2
- Treatment: CHATO Training Module 3
 - Communication Rating Sheet Post-Test
 - CHATO Post-Test
 - Modified Duke Diffusion of Innovation Intention Survey

- CHATO Program Evaluation

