10 DATA COLLECTION AND QUALITY ASSURANCE

10.1 Data Collection Forms

Data will be collected according to Table 4. The data itself will be collected via the Moodle learning system managed by the Instructional Designer or RedCAP managed by the Project Director. The person responsible for collection will send data to the data manager for data cleaning and analysis. The data manager is the individual designated for managing data files and for assuring confidentiality. She will provide data directly to the DSMB and Program Officer upon request. She will serve as the data coordinator for the study.

TABLE 4. Data Collection Forms, Method of Collection, and Person Responsible.

Data Collection Form	Method of Collection	Person Responsible
NH Agreement/Letter of Support	NH Leadership/Word	Project Director
Staff CHATO Participation	NH Leadership/Excel	Project Director
Staff Demographics	CHATO Training/Moodle	Instructional Designer
Staff CHATO Knowledge Pre-Test	CHATO Training/Moodle	Instructional Designer
Communication Rating Sheet Pre-Test	CHATO Training/Moodle	Instructional Designer
Staff CHATO Knowledge Post-Test	CHATO Training/Moodle	Instructional Designer
Communication Rating Sheet Post-Test	CHATO Training/Moodle	Instructional Designer
Modified Duke Diffusion of Innovation Intention Survey	CHATO Training/Moodle	Instructional Designer
Staff CHATO Evaluation	CHATO Training/Moodle	Instructional Designer
Implementation Survey	NH Leadership/RedCAP	Project Director
The Artifacts of Culture Change Tool	NH Leadership/RedCAP	Project Director
Staff Wage Data	NH Leadership/RedCAP	Project Director
NH Level Resident Data	NH Executives/Internal Data System	Project Director
Leadership Phone Interviews	NH Leadership/Phone Interview	LeadingAge Evaluators

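### Wait-list staff need pre-tests at Time 1 and Time 2, but the only delivery route described is inside Module 1 during each home's own training period

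*Combined protocol and SAP*

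**What the plan says.** **What the design needs.** Section 3 states: "At time 1, nursing home staff in both groups will complete baseline pre-tests of knowledge and rating of communication". It then has the wait-list arm repeat both pre-tests at Time 2, before starting the modules. Table 1 shows the same sequence. Section 9.4 compares the Time 1 to Time 2 change in knowledge between arms with a linear mixed model.

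**Where the tests sit.** Section 6.2.3 lists "CHATO Knowledge Pre-Test" and the communication rating pre-test under "Treatment: CHATO Training Module 1". Section 5.1 agrees: "The modules contain pre and posttests (scenario-based questions and rating of staff communication in video clips) to evaluate knowledge gain from CHATO". Table 4 in Section 10.1 gives "CHATO Training/Moodle" as the collection method for both pre-tests and no other. Section 2.2 describes the site that hosts the modules as "a free and publicly available learning portal".

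**When a home gets access.** Section 5.1 releases the training link to homes at three-monthly steps set by the randomisation. Section 6.2.2 obtains the letter of agreement and the staff email list at a meeting that opens the home's own three-month period, and the system then emails the link. Section 6.1 schedules the pre-tests once, in the second month of that period.

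**What is monitored.** Under Section 5.1, "metrics including time spent in each module are collected for analyses". Section 5.4 has the instructional-design team monitor time in the modules, and Section 10.3.5 has the systems reviewed daily.

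**The concern.** The primary outcome is knowledge gain. Of the two knowledge analyses planned, only the Time 1 to Time 2 comparison uses the randomisation. The other pools pre- to post-training change over both arms. The randomised comparison needs a Time 1 score and an untrained Time 2 score from the wait-list homes. The plan asks for both in Section 3, yet its operational sections describe no way to collect the Time 1 score that keeps those staff outside the training module. What is at stake is whether the wait-list change score exists at all and, if it does, whether it comes from staff who have not yet seen the content.

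**Working it through.** There is no stated power or sample-size calculation to reproduce. The 150 in Section 9.2 is an accrual estimate. The check is a comparison of what the design requires with what the operational sections supply.

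1. **Pre-tests required and supplied, per home.**

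| Arm | Required (Table 1) | Supplied (Sections 6.1, 6.2.3) | Shortfall |
|---|---|---|---|
| Immediate | 1 (Time 1) | 1 | 1 − 1 = 0 |
| Wait-list | 2 (Time 1, Time 2) | 1 | 2 − 1 = 1 |

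2. **Which one is missing.** The scheduled pre-test comes just before training, so for a wait-list home it matches the repeat baseline. The Time 1 test has no place. As an illustration, assume that the two arms' three-month periods run back to back, which fits the six-month pilot in Section 8 (3 + 3 = 6). Immediate homes are then tested in study month 2, and wait-list homes in study month 3 + 2 = 5. In month 2 a wait-list home has not had its initial meeting, so under Section 6.2.2 the team holds neither its staff list nor, at the time given there, its letter of agreement.

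3. **Ways to follow the text.**
   - *Keep to the staggered release.* Wait-list staff have no Time 1 score, and the planned comparison of change cannot be made from observed data. What remains is a comparison of Time 2 levels across three homes against three, which leans on baseline balance that six clusters cannot be relied on to give.
   - *Release the link early.* Wait-list staff enter Module 1 to be tested. Let D be the true training effect, c the share of wait-list staff who reach content before Time 2, and f the fraction of the benefit that they gain. The expected contrast is D × (1 − c × f), which is at most D when D is positive. If Time 2 serves as the wait-list pre-training score, that arm's pre-to-post gain in the pooled analysis also falls by about c × f × D. The documents give no value for c or f, and no between-arm estimate of D.
   - *Release the tests alone in Moodle.* This would work. The documents neither state it nor rule it out.

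4. **Stated safeguards.** Section 5.1 requires exercises to be passed before a user moves on, but this depends on neither arm nor date. Section 5.3 bars other communication programmes, not early use of CHATO. Section 9.4 analyses module time and completion, but no rule uses the logs to identify wait-list access before Time 2.

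**The case against.** The strongest reply is that this is a delivery detail, not a contaminated arm. The staggered link release is an access control. Section 3 treats the repeat pre-test as a step before the modules. Sitting a test at the start of Module 1 is not the same as seeing the content. Whole homes are randomised, which limits spillover within a home, and any bias is toward no difference. The Implementation Toolkit and Training Overview appear in Section 15 only as headings, so they may settle access in text that cannot be checked here.

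Much of that stands, and it rules out several stronger readings that a reader might infer:

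- *Wait-list staff must enter the course early.* Not established. Sections 5.1 and 6.2.2 withhold the link until the home's own period, and Moodle tests might be released alone.
- *The course is open to anyone.* Section 2.2 calls the hosting site "a free and publicly available learning portal". It does not say that CHATO allows self-enrolment. Section 6.2.2 describes links emailed to listed staff, and Section 10.3.3 describes accounts and log-ins.
- *Early access would go unseen.* Module time is logged, systems are reviewed daily, and Section 10.3.4 counts giving a participant the wrong treatment as a deviation. Only a planned analytic use of the logs is missing.
- *The dilution can be sized.* The only earlier CHATO knowledge gain (Section 2.2) is an uncontrolled pre-post change in nine university-affiliated people. Any exposed share would be invented.

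What the reply does not supply is a route to the Time 1 score. The stagger that prevents early exposure is also what leaves the wait-list arm without that test.

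**Conclusion.** The concern holds as an unreconciled conflict. Section 3 and Table 1 require two pre-training tests from wait-list staff. Sections 5.1, 6.1, 6.2.2, 6.2.3 and 10.1 together supply one, inside Module 1, in the home's own period. As written, either the Time 1 score is missing or it is collected through a module with no stated lock on its content. If content is reached early, the randomised contrast moves toward no difference. The size of that movement cannot be estimated from the documents, and contamination is not shown to occur. The conclusion rests on reading the operational sections literally and on the access rules not being set out in the appendices. It should be settled before launch, because a missing Time 1 score cannot be recovered later.

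**What to change.** Reconcile Section 3 with Sections 5.1, 6.1, 6.2.2 and 6.2.3 as follows:

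1. Obtain each wait-list home's agreement and staff list before Time 1. Show the exempt statement before the first test, since Section 11.2 now ties it to the first module.
2. Deliver the Time 1 and Time 2 pre-tests as a stand-alone Moodle quiz outside Module 1, and add both wait-list time points to the Section 6.1 schedule.
3. Open module content by home, only after that home's last pre-training test.
4. State in Section 9.4 that the existing module-time logs will be used to report any wait-list content access before Time 2, with those staff analysed in the arm to which their home was randomised.

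The cost is minor learning-system set-up by the existing instructional-design team, an earlier administrative contact with three homes, and short text edits. Section 6.2.2 describes its agreement procedure as IRB-approved, so the change in timing may need to be notified.
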